### **Continuous Variable Assessed at Multiple Time Points (11 endpoints):**

- **Secondary Endpoint:** Change from baseline (post-baseline minus baseline) in HbA1c reported for each pre-specified study visit.
- **Secondary Endpoint:** Change from baseline (post-baseline minus baseline) in Fasting plasma glucose (FPG) reported for each pre-specified study visit.
- **Secondary Endpoint:** Change from baseline (post-baseline minus baseline) in Insulinresistance by HOMA-IR reported for each pre-specified study visit.
- **Secondary Endpoint 6a:** Change from baseline (post-baseline minus baseline) in Post-prandial plasma glucose (PPG) reported for each pre-specified study visit.
- **Secondary Endpoint 6b:** Change from baseline (post-baseline minus baseline) in beta cell function reported for each pre-specified study visit.
- **Secondary Endpoint 6c:** Change from baseline (post-baseline minus baseline) in disposition index reported for each pre-specified study visit.
- **Secondary Endpoint:** Change from baseline in blood pressure by visit.
- Secondary Endpoint: Change in lipid profile from baseline by visit: total cholesterol
- Secondary Endpoint: Change in lipid profile from baseline by visit: triglycerides

- Secondary Endpoint: Change in lipid profile from baseline by visit: HDL
- Secondary Endpoint: Change in lipid profile from baseline by visit: LDL
- Secondary Endpoint: Change in weight from baseline (post-baseline minus baseline) by visit. Weight will be evaluated based on the intra-patient percent change from baseline. (% TBWL: % Total Body Weight Loss)
- Secondary Endpoint: Time in Range (TIR) based on Continuous Glucose Monitoring (CGM) by visit

For each set of results for each Comparison Set, the following 2 research questions will be addressed. Results will be presented using the Level 3 tables b through e.

For each endpoints measured on a continuous scale, what are the overall estimates in the FAS population assessed over time.

For each endpoint measured on a continuous scale, is there a difference in the estimates in the FAS population based on the generation of the device, voltage, and single vs. double treatment assessed over time?

The list of the top-line tables to be generated are presented below:

Table 14.4.1 entitled Overall Summary of Procedure Success and Procedure Time (FAS Population)

Table 14.4.2 entitled Overall Summary of HbA1C, Fasting plasma glucose (FPG), Insulinresistance by HOMA-IR, and Post-prandial plasma glucose (PPG) by Visit (FAS Population)

Table 14.4.3 entitled Overall Summary of Beta Cell Function by Visit (FAS Population)

Table 14.4.4 entitled Overall Summary of HbA1c improvement  $\geq 0.3$  points by Visit (FAS Population)

Table 14.4.5 entitled Overall Summary of Percent Change in Body Weight by Visit (FAS Population)

Table 14.4.6 entitled Overall Summary of Glucose-Lowering Medications by Visit (FAS Population)

Table 14.4.7 entitled *Overall Summary of Liver Enzymes and Lipids by Visit (FAS Population)* 

Table 14.4.8 entitled Overall Summary of Blood Pressure Measurements by Visit (FAS Population)

Table 14.4.9 entitled Overall Summary of Continuous Glucose Monitoring (CGM) by Visit (FAS Population)

Version 1.0 Confidential Page 35 of 42

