Secondary Endpoints	 Procedure success rate defined as the proportion of participants who successfully received the target treatment of at least 6 cm of duodenum treatment Procedure time defined as the time between the Endogenex catheter insertion and catheter removal. Change from baseline in glycemic parameters post procedure by visits HbA1c Fasting plasma glucose (FPG) Insulin resistance by HOMA-IR Post prandial plasma glucose (PPG), Beta cell function, disposition index by mixed meal tolerance test (MMTT) Time in range, glucose variability by continuous glucose monitoring (CGM) Proportion of treated participants with an HbA1c improvement ≥0.5 points from baseline at 24 weeks Proportion of treated participants with an HbA1c improvement ≥0.5 points from baseline at 24 weeks and maintained at 48 weeks Change in weight from baseline by visit Change in glucose-lowering medication usage Change in liver enzymes from baseline at 24 weeks Alanine Aminotransferase (ALT) Aspartate Aminotransferase (AST) Change from baseline in blood pressure and lipid profile by visit 		
Safety Evaluation	Safety will be characterized through a summary of the incidence of adverse events, device- or procedure-related adverse events, and serious device- or procedure-related		
	adverse events.		
Inclusion Criteria	1. 22-65 years of age		
	2. Current diagnosis of T2D3. History of T2D for at least 3 years and less than or equal to 10 years		
	3. History of T2D for at least 3 years and less than or equal to 10 years		

- 4. HbA1C of 7.5-10.0%, inclusive
- 5. BMI 24-40 kg/ m^2 , inclusive
- 6. On two to three non-insulin glucose lowering mediations, with one at maximum tolerated dose and another at half-maximum dose at least, with no changes in medication for at least 12 weeks prior to baseline visit prior to baseline visit
- 7. History of failed attempt to reach glycemic goal by lifestyle modifications
- 8. Weight stability (defined as a < 5% change in body weight) for at least 12 weeks prior to the screening visit
- 9. Agree not to donate blood during participation in the study.
- 10. Able to comply with study requirements and understand and sign the Informed Consent Form
- 11. Women of childbearing potential must be using an acceptable method of contraception throughout the study
- 12. Willing and able to use CGM for the duration of the study and comply with study visits and study tasks as required per protocol.

13.

Exclusion Criteria

- 1. Diagnosed with type 1 diabetes

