3 STUDY OBJECTIVES AND ENDPOINTS

The objective of this FIH study is to assess the feasibility and preliminary safety of the Endogenex Device for endoscopic duodenal mucosal regeneration in individuals with type 2 diabetes inadequately controlled on 2-3 non-insulin glucose-lowering medications.

The study will also assess, as exploratory endpoints, treatment efficacy, evaluated by changes in glycemic control and liver enzymes post procedure from baseline.

Objectives	Endpoints
Primary	
To assess the safety of the Endogenex Device for DMR procedure	Proportion of participants experiencing one or more device- or procedure-related serious adverse events at 12 weeks post procedure.
Secondary	
To assess the technical feasibility of the Endogenex Device for DMR procedure	 Procedure success: defined as successful treatment of at least 6 cm of duodenum segment. Procedure time: defined as the time between the Endogenex catheter insertion and the catheter removal.
To assess changes in glycemic control	 Change from baseline in glycemic parameters post index procedure, by visits
To assess changes in liver enzymes	 HbA1c Fasting plasma glucose (FPG) Insulin-resistance by HOMA-IR Post prandial plasma glucose (PPG), Beta cell function, disposition index by mixed meal tolerance test (MMTT) Time in range, glucose variability by continuous glucose monitoring (CGM) Proportion of treated participants with an HbA1c improvement of 0.5% or more at 24 weeks from
	 Proportion of treated participants with an HbA1c improvement of 0.5% or more at 24 weeks from baseline and maintained at 48 weeks Change in weight from baseline by visit Change in glucose-lowering medication usage Change in liver enzyme from baseline at 24 weeks Alanine Aminotransferase (ALT)

	o Aspartate Aminotransferase (AST)
•	Change from baseline in blood pressure and lipid profile by visit

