12.4.4 Effectiveness Analysis

Secondary endpoints are summarized in Section 3. The primary analysis of the study's secondary endpoints will be performed using the mITT population. The analysis will also be performed using the PP population when appropriate.

Results for these endpoints will be tabulated and reported for each treatment arm at each timepoint for which data were specified to be collected, using change scores from baseline where appropriate. For binary outcomes, Fisher's exact test will be used to assess differences which may be present between groups, while t-tests or Wilcoxon's rank-sum will be applied for continuous outcomes depending on the normality assumption. Effectiveness endpoints collected at multiple timepoints post-intervention (e.g., HbA1c) will also be assessed longitudinally using repeated-measures mixed-effects models with time as the repeated measure and treatment arm as a factor variable. Assessment of overall change from baseline and comparisons between treatment arms will then be predicated principally upon these repeated-measures analyses.

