### **Seventh Secondary Endpoint**

The distribution of this endpoint is continuous. The primary population for analysis of this endpoint will be the FAS population. The estimates will be derived using a mixed model repeated measure procedure; the 12 week result will be the principal time point of interest.

Time in range, glucose variability by continuous glucose monitoring (CGM)

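### The SAP drops the change from baseline from the CGM endpoint and lists only time in range for analysis, so neither the model response nor the handling of glucose variability is settled

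*SAP*

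**What the plan says.** **Protocol.** Section 3 has a parent entry, "Change from baseline in glycemic parameters post index procedure, by visits", and the CGM item "Time in range, glucose variability by continuous glucose monitoring (CGM" is one of the measures listed under it. The Protocol Summary has the same structure, with the parent worded "Change from baseline in glycemic parameters post procedure by visits". Section 12.4.4 calls for tabulation "using change scores from baseline where appropriate". It then rests the assessment of overall change, and the comparison of arms, mainly on repeated-measures models.

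**SAP.** The endpoint appears in three places:

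- Section 4.2.1 (Seventh) names both CGM measures, with no change from baseline, no model and no time point.
- Section 9 (Seventh) names both measures, again with no change, and adds: "The estimates will be derived using a mixed model repeated measure procedure; the 12 week result will be the principal time point of interest".
- Section 9.2 (continuous, multiple time points) has the single entry "Time in Range (TIR) based on Continuous Glucose Monitoring (CGM) by visit". It contains neither change nor variability.

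The neighbouring entries in 9.2 are explicit, for example "Change from baseline (post-baseline minus baseline) in HbA1c reported for each pre-specified study visit". Results of that list go to Level 3 tables. The template for these in SAP Section 7 has rows for baseline, post-procedure visit and change. Table 14.4.9 covers CGM by visit.

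**The concern.** The glycemic objective is to assess changes in glycemic control, and every patient is treated. A modelled Week 12 mean of TIR does not by itself show whether TIR moved.

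The SAP also compares device groups: 3 versus 7 versus 10, and 3 versus 17. These groups were filled in sequence and not randomised, so they may differ at baseline systematically as well as by chance. A contrast of unadjusted levels carries such differences forward. SAP 7.2 names no covariate for the models.

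Variability is named in two sections and absent from the list that drives the analysis. The programmer is left to decide whether it is modelled, and with which measure.

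**Working it through.** **1. Is the omission specific to CGM?** The 9.2 list has 13 entries under a heading that says 11. Twelve are written as changes, and the CGM entry is the only one that is not. The list is loosely edited, but the missing change is confined to this endpoint and recurs in all three places.

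**2. Is the response stated elsewhere?** No. The SAP gives no repeated-measures code and no response variable for this endpoint. It defines neither TIR nor a variability measure.

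**3. What does a level leave open?** Take a Week 12 mean TIR of 50%.

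- Baseline 50%: change = 50 − 50 = 0.
- Baseline 40%: change = 50 − 40 = +10 points.

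The same level fits both.

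**4. Size of baseline imbalance between groups.** The plan has no figure to reproduce beyond the group sizes, 3 + 7 + 10 = 20. The standard error (SE) of a chance baseline mean difference, in SD units, is √(1/n₁ + 1/n₂). The probability column uses a normal approximation with equal SDs and exchangeable groups.

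| Groups | SE (SD units) | P(imbalance > 0.5 SD) |
|---|---|---|
| 3 vs 7 | 0.690 | 0.469 |
| 3 vs 10 | 0.658 | 0.448 |
| 7 vs 10 | 0.493 | 0.310 |
| 3 vs 17 | 0.626 | 0.425 |

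**5. In TIR points.** Assumed, because the documents give neither: SD 20 to 25 points, equal at baseline and follow-up, and correlation r of 0.6 to 0.8.

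- SE of the level contrast, 7 vs 10: 0.493 × 20 = 9.9 to 0.493 × 25 = 12.3.
- SE of the change contrast = SE(level) × √(2(1 − r)): 9.9 × 0.632 = 6.2 to 12.3 × 0.894 = 11.0.
- With no true difference, a 1-SE baseline imbalance leaves r × SE(level) in the level contrast. For 7 vs 10 this is 0.6 × 9.9 = 5.9 to 0.8 × 12.3 = 9.9. For 3 vs 17 it is 0.6 × 12.5 = 7.5 to 0.8 × 15.7 = 12.5.
- A raw change score leaves (1 − r) × SE(level) with the opposite sign. For 7 vs 10 this is 0.2 × 9.9 = 2.0 to 0.4 × 12.3 = 4.9. For 3 vs 17 it is 0.2 × 12.5 = 2.5 to 0.4 × 15.7 = 6.3.

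**6. Does change gain precision?** Ratios to the level SE, before any loss of degrees of freedom:

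| r | Raw change, √(2(1 − r)) | Baseline-adjusted, √(1 − r²) |
|---|---|---|
| 0.3 | 1.18 | 0.95 |
| 0.5 | 1.00 | 0.87 |
| 0.7 | 0.77 | 0.71 |
| 0.9 | 0.45 | 0.44 |

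A raw change score is more precise than a level only if r exceeds 0.5. Adjustment for baseline does not need that condition. Under a linear model it also removes the expected contribution of the observed baseline imbalance.

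**The case against.** The best defence is that the SAP never says the response is the level, and that other text points to change. The SAP is to be read with the protocol, whose 12.4.4 calls for change scores where appropriate. The SAP's own objective is to assess changes, and the Level 3 template has a change row. A reporting schedule by visit is compatible with a change, and a repeated-measures model that includes the baseline visit would estimate change directly. This stands as far as it goes: the fault is an unstated response, and modelling of the level is the plain reading of 9.2, not an explicit instruction. It does not close the gap. The Level 3 row is descriptive, whereas 12.4.4 rests the assessment of change on the model. No model with baseline as a visit is written down.

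Two stronger readings are tempting, and the documents support neither.

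- A reader might infer that variability has been removed and will get no estimate. Sections 4.2.1 and 9 both keep it, Section 9 assigns it to the mixed model, and Table 14.4.9 is not limited to TIR. This is an inconsistency within the SAP.
- A reader might infer that the level fails because it is not a treatment effect, and that change would be one. With no control arm, a change from baseline is not a treatment effect either. Protocol 2.5.1 lists lifestyle counseling, CGM and medication monitoring alongside the device, and regression to the mean adds to these.

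The stakes are also modest. SAP 7.1 calls the testing informative only, and SAP 9 states that there are no formal hypothesis tests.

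**Conclusion.** The point holds as a mismatch between protocol and SAP, combined with an inconsistency inside the SAP. The protocol endpoint is change from baseline in two CGM measures. The SAP omits the change everywhere and lists one measure for analysis. Followed literally, 9.2 yields a TIR level. That is not a within-patient change, and it mixes baseline differences into the group comparisons.

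Under the assumed SD and correlation, a 1-SE baseline imbalance would leave about 6 to 10 TIR points in the 7 versus 10 level contrast, and about 7.5 to 12.5 points in 3 versus 17, with no true difference. These figures are illustrative: the SD and correlation are not in the documents. The mismatch in wording depends on neither. No stated figure in the plan changes, and the primary safety endpoint is untouched. It should be corrected before analysis, as a low-stakes secondary endpoint.

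**What to change.** In SAP 4.2.1, Section 9 (Seventh) and 9.2, replace the CGM entry with two endpoints:

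1. change from baseline in TIR, post minus baseline;
2. change from baseline in a named glucose-variability measure (for example CV%), post minus baseline.

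Spell out the subtraction, because SAP Section 7 also defines a ratio form of change. Define both measures and the CGM averaging window.

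Fit each endpoint with the repeated-measures model, using change as the response and the patient's baseline value as a covariate. Record that covariate in SAP 7.2. Report both endpoints in Table 14.4.9.

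The cost is SAP wording, one extra derived variable and one model degree of freedom in a 20-patient study. No new data are needed: the protocol already requires at least 5 days of CGM at baseline and CGM through 48 weeks. The repair gives an adjusted within-patient change. It does not turn an uncontrolled change into a device effect, and the report should say so.

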### 10. SAFETY

The following sections describe how the safety results will be analyzed and reported. The safety analyses will be conducted using the ITT population, defined as all patients in whom the endoscopic screening procedure was initiated. In addition to the reporting of adverse events, Safety will include an examination of hypoglycemia, pancreatic enzymes, and endoscopic follow-up.

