### 3. INTRODUCTION

This statistical analysis plan (SAP) describes the planned statistical methods to be used during the reporting and analysis of data collected under the Clinical Investigation Protocol entitled Safety and Feasibility of Endoscopic Application of a Novel Therapy for Duodenal Mucosal Regeneration in the Treatment of Type II Diabetes (REGENT-1-US Study), Doc. No. 346. This SAP should be read in conjunction with the study protocol and case report forms (CRFs).

The REGENT-1-US study is a multicenter, open-label, treatment-only study conducted in the United States. The study is designed to assess the feasibility and preliminary safety of the Endogenex device for endoscopic duodenal cellular regeneration in patients with type 2 diabetes (T2D) inadequately controlled on glucose-lowering medications. The protocol enrolled patients who were treated with non-insulin glucose-lowering agents; a tabulation of the treatment and number of patients is presented below.

Device Generation 1 / 600	Device Generation 1 / 600	Device Generation 2 / 750	All
Volts / Single Treatment	Volts / Double Treatment	Volts / Double Treatment	Patients
(n)	(n)	(n)	(n)
3	7	10	20

This plan is developed for analysis and reporting of the 48-week follow up data. The SAP may be revised in the future to address additional follow up data analysis beyond 48 weeks, if necessary.

Patients are considered enrolled in the study once the patient has passed endoscopic screening and proceeded to the Index procedure. *Screen failures* are defined as patients who consented to participate in the clinical study and started the screening tests specified by the protocol but are not subsequently enrolled into the study. Procedure success was defined as at least 6cm of duodenum was successfully treated.

The following analysis populations are defined for the presentation of the results from this study: *Intent-to-Treat* (ITT), *Full Analysis Set* (FAS) [referred to in the study protocol as the modified Intent-to-Treat (mITT) population], *Per-Protocol* (PP) and *Completed Cases* (CC). (Ref. Section 11.3 of the study protocol).

The primary and secondary safety analyses will be performed using the ITT population. The primary effectiveness analyses will be performed using the FAS population. The Per-Protocol population and Completed-Cases population will be used for the sensitivity analyses of the primary and secondary effectiveness endpoints.

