*Intent-to-Treat*: The Intent-to-Treat population includes all enrolled patients, regardless of the patient having received the target treatment (at least 6cm of duodenum treated). The point of enrollment occurs when a patient has provided written informed consent and an energy delivery has been attempted during the index procedure.

*Full Analysis Set*: The FAS population consists of the ITT population patients who received the target treatment (at least 6 cm of duodenum treatment) and that have at least one post-treatment follow-up examination.

**Per-Protocol**: The Per-Protocol population is a subset of the FAS population and includes all patients who received the target treatment, do not have any major eligibility violations, and maintained stable glucose-lowering medications for 24 weeks post-procedure. The definition of what constitutes a major eligibility violations will be established before the study database is locked.

**Completed Cases**: The Completed Cases population is a subset of the Per-Protocol population and includes all patients who received the target treatment, do not have any major eligibility violations, and maintained stable glucose-lowering medications for 24 weeks post-procedure, and completed the final Week 48 End of Study Visit.

The details contained in this plan include the source code for the assessment of poolability across a myriad of factors and the analysis of each of the endpoints. Additionally, the structure of the table designs and a comprehensive index of the tables and listings has been provided.

This document contains information to support the generation of a Clinical Study Report (CSR). The planned analyses identified in this SAP may be included in regulatory submissions, medical presentations, and manuscripts. Exploratory analyses, not identified in this SAP, may be performed to support the clinical development program. Any post-hoc or unplanned analyses that are performed, but not identified in this SAP, will be clearly identified in the final report of the results. The structure and content of this SAP are designed to meet the requirements identified by the FDA and the International Conference on Harmonization (ICH) Guidance on Statistical Principles for Clinical Trials.

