### 5. STUDY OVERVIEW

## 5.1. Study Design and Description of the Study Device

This is a multicenter, open-label, treatment-only study conducted in the United States. A total of 20 participants is planned for the study. The study will test two treatment parameters. The first 10 participants will be treated at a generator setting of 600 Volts/ (600V) and the second group of 10 participants at 750 Volts/ (750V). In the 600V group, the first 5 participants will be enrolled/treated with the investigational device sequentially with at least 14 days observation time between each procedure. In the 750V group, the first participants will be enrolled/treated with the investigational device sequentially with at least 6 days observation time between each procedure.

Participants with T2D inadequately controlled on 2-3 non-insulin glucose-lowering medication(s) will be screened for study eligibility. Eligible participants who consent to participate in the study will maintain his/her background glucose-lowering medication(s) stable (no medication or dose change) for at least 12 weeks prior to baseline visit.

The index procedure will be performed under general anesthesia or deep sedation and within 21 days from the baseline visit. Participants will undergo endoscopic screening immediately prior to the DMR procedure, and eligible participants will undergo the DMR procedure. Participants may be discharged per local hospital's guideline; an overnight stay is not required but allowed per local policy and investigator's clinical judgement. A participant is enrolled in the study when the Endogenex catheter insertion is attempted. Participants excluded during endoscopic screening will be considered a screen failure and will be followed for four weeks after the procedure for safety.

Post index procedure, participants will be on a transitional diet consisting of clear liquids for 24 hours followed by a full liquid diet for 3 days, pureed food for 3 days, and soft food for one week, and then return to normal food as tolerated.

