### 6. ANALYSIS POPULATIONS

Patients will be considered enrolled in the study once the patient has passed endoscopic screening. Screen failures are defined as patient who consented to participate in the clinical study and started the screening tests specified by the protocol but are not subsequently enrolled in the study.

The primary and secondary safety analyses will be performed using the ITT. The primary effectiveness analyses will be performed using the FAS population. The Per-Protocol population and Completed-Cases population will be used for the sensitivity analyses of the primary and secondary effectiveness endpoints.

*Intent-to-Treat*: The Intent-to-Treat population includes all enrolled patients, regardless of the patient having received the target treatment (at least 6cm of duodenum treated). The point of enrollment occurs when a patient has provided written informed consent and an energy delivery has been attempted during the index procedure.

*Full Analysis Set*: The FAS population consists of the ITT population patients who received the target treatment (at least 6 cm of duodenum treatment) and that have at least one post-treatment follow-up examination.

**Per-Protocol**: The Per-Protocol population is a subset of the FAS population and includes all patients who received the target treatment, do not have any major eligibility violations, and maintained stable glucose-lowering medications for 24 weeks post-procedure. The definition of what constitutes a major eligibility violations will be established before the study database is locked.

**Completed Cases**: The Completed Cases population is a subset of the Per-Protocol population and includes all patients who received the target treatment, do not have any major eligibility violations, and maintained stable glucose-lowering medications for 24 weeks post-procedure, and completed the final Week 48 End of Study Visit.

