All mean and median values will be formatted to one more decimal place than the measured value. Standard deviation values will be formatted to two more decimal places than the measured value. Minimum and maximum values will be presented with the same number of decimal places as the measured value.

The number and percentage of responses will be presented in the form XX (XX.X%).

Version 1.0 Confidential Page 19 of 42

- All summary tables will include the analysis population sample size (i.e., number of patients).
- Relative Study Day 1 is defined as the day the patient underwent the DMR study procedure. All study days are determined relative to the day the patient underwent the DMR study procedure.
- Baseline values will be defined as those values recorded immediately prior to the DMR study procedure.
- Change from baseline for ratio data will be calculated as follows:

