### **Primary Endpoint**

The primary endpoint of the study is predicated on safety; the distribution of this endpoint is binary. The primary population for analysis of this endpoint will be the ITT population.

Proportion of patients experiencing one or more device- or procedure-related serious adverse events at 12 weeks post-procedure.

All device-related or procedure-related serious adverse events from the start of the study procedure through relative study day 84 will be used in the tabulation.

The secondary endpoints are listed below:

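### The SAP defines the ITT population, the denominator of the primary safety endpoint, in conflicting ways, and two of them depart materially from the protocol

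*SAP*

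**What the plan says.** **Protocol.** Section 12.3 assigns the primary safety analysis to the ITT population, meaning everyone enrolled under Section 5.3. Section 5.3 sets enrolment at written consent plus an attempted insertion of the study catheter.

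**SAP.** The primary endpoint is also assigned to the ITT population (Sections 9 and 9.1), but membership is described in five ways:

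- Section 5.1: "A participant is enrolled in the study when the Endogenex catheter insertion is attempted". This matches the protocol.
- Section 3, introductory text: "Patients are considered enrolled in the study once the patient has passed endoscopic screening and proceeded to the Index procedure". This nearly coincides with the protocol.
- Section 6, opening sentence: "Patients will be considered enrolled in the study once the patient has passed endoscopic screening".
- Sections 3 and 6, inside the ITT definition itself: "The point of enrollment occurs when a patient has provided written informed consent and an energy delivery has been attempted during the index procedure".
- Section 10: "The safety analyses will be conducted using the ITT population, defined as all patients in whom the endoscopic screening procedure was initiated".

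On patients excluded at endoscopy, Section 5.1 says: "Participants excluded during endoscopic screening will be considered a screen failure and will be followed for four weeks after the procedure for safety".

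**The concern.** The two outlying rules err in opposite directions.

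**Energy delivery attempted** is narrower than the protocol. A patient in whom the catheter was inserted and the case then abandoned would leave both numerator and denominator. Several harms anticipated in protocol Section 2.5.2, such as upper GI trauma, perforation, aspiration and anaesthetic complications, can occur before any energy is delivered. An ITT safety set should keep such patients.

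**Endoscopic screening initiated** is wider. It brings in patients never exposed to the device, with four weeks of follow-up against an endpoint window running "from the start of the study procedure through relative study day 84". Such patients have no reference day either, because "Relative Study Day 1 is defined as the day the patient underwent the DMR study procedure". They also have no device generation, voltage or treatment group, so they could appear only in the column for all patients.

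Read literally, the primary table (14.4.1, SAP Section 9.1) and the related-SAE table (14.3.10.1, SAP Section 10.1.4) could carry the same ITT label over different denominators.

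**Working it through.** **Step 1: who is in under each rule**

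| Patient | Protocol 5.3, SAP 5.1 | SAP 3 and 6 (energy attempted) | SAP 6 (passed screening) | SAP 3 (passed and proceeded) | SAP 10 (screening initiated) |
|---|---|---|---|---|---|
| Excluded at endoscopy | out | out | out | out | in |
| Passed endoscopy, no insertion attempted | out | out | in | unclear | in |
| Insertion attempted, no energy attempted | in | out | in | in | in |
| Energy delivery attempted | in | in | in | in | in |

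The rules agree only on the last row. Section 10 also contradicts the SAP's own statements that patients excluded at endoscopy are screen failures and that screen failures are not enrolled.

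**Step 2: the plan's own figure.** The table in SAP Section 3 gives 3 + 7 + 10 = 20, which equals the planned number in protocol Section 12.2. It does not say which rule produced the 20.

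**Step 3: effect on the primary proportion.** The estimate is x/n. The exact (Clopper-Pearson) 95% limits are:

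- lower = 0.025 quantile of Beta(x, n − x + 1), or 0 when x = 0
- upper = 0.975 quantile of Beta(x + 1, n − x), which is 1 − 0.025^(1/n) when x = 0

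For example, 0/20 gives 1 − 0.025^(1/20) = 16.8% and 0/25 gives 1 − 0.025^(1/25) = 13.7%.

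The documents report neither event counts nor numbers of catheter-only patients or endoscopic screen failures. All event counts, one catheter-only patient, and 5 or 10 screen failures are therefore assumptions.

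| Scenario | Protocol rule | Alternative rule |
|---|---|---|
| Energy rule; the dropped patient had the only SAE | 1/20 = 5.0% (0.1 to 24.9) | 0/19 = 0% (0 to 17.6) |
| Energy rule; the dropped patient had no SAE | 1/20 = 5.0% (0.1 to 24.9) | 1/19 = 5.3% (0.1 to 26.0) |
| Same, one voltage group; dropped patient had the only SAE | 1/10 = 10.0% (0.3 to 44.5) | 0/9 = 0% (0 to 33.6) |
| Same, one voltage group; dropped patient had no SAE | 1/10 = 10.0% (0.3 to 44.5) | 1/9 = 11.1% (0.3 to 48.2) |
| Section 10; 5 screen failures, no added event | 2/20 = 10.0% (1.2 to 31.7) | 2/25 = 8.0% (1.0 to 26.0) |
| Section 10; 10 screen failures, no added event | 2/20 = 10.0% (1.2 to 31.7) | 2/30 = 6.7% (0.8 to 22.1) |
| Section 10; no events at all, 5 or 10 screen failures | 0/20, upper limit 16.8% | 0/25 or 0/30, upper limit 13.7% or 11.6% |
| Section 10; 5 screen failures, one with a procedure-related SAE | 2/20 = 10.0% (1.2 to 31.7) | 3/25 = 12.0% (2.5 to 31.2) |

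The Section 10 rows apply to the all-patients column only. The rate can move either way under either rule.

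**The case against.** The strongest reply has five parts.

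1. **Reach of Section 10.** Its sentence introduces the 14.3.x adverse event tables. The primary endpoint is specified in Section 9 and populations in Section 6, so the clause may be a stray. This stands as a limit on what Section 10 governs directly. But it is worded as a definition of ITT, and Section 9.1 uses the same label.
2. **Little room for an affected patient.** The 20-patient table is in the past tense and classes everyone as singly or doubly treated, which a catheter-only patient would not naturally fit. This is fair evidence that the actual effect may be small. It does not exclude such a patient, for instance one classed by planned group.
3. **The 3/25 case.** Protocol Section 12.4.3 counts only events at or after the index procedure, and Section 4.1 puts endoscopic screening immediately before the DMR procedure. Section 6.1, however, puts endoscopic assessment at the beginning of the procedure, and the SAP counts from the start of the study procedure. That scenario is arguable, not excluded.
4. **No decision depends on it.** There is no performance goal or formal test, and the stopping rules count events rather than ITT proportions. Most of the shifts are small beside the intervals. This limits the severity. Patient accounting and full listings would also let a careful reader spot an affected patient.
5. **The protocol already settles it.** The SAP is to be read together with the protocol, but that is not a rule of precedence where the SAP gives its own definition. The SAP also cites protocol Section 11.3 for the populations, whereas they stand in 12.3. The sponsor should confirm which protocol version was the source.

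**Conclusion.** The concern holds. The SAP contradicts itself and the protocol on who belongs to the population for its only primary endpoint. The rules for energy delivery attempted and endoscopic screening initiated are real departures, one narrower and one wider. The two other screening-based wordings matter less.

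With 20 patients, one catheter-only case could decide whether the reported rate is zero. More ordinary shifts are a fraction of a percentage point to about three points in the estimate. The zero-event upper limit could fall by about three to five points (16.8% to 13.7% or 11.6%). These sizes depend on assumed counts, and if no patient falls between the rules every version gives the same result. Effectiveness analyses on the full analysis set are not affected, because anyone with at least 6 cm treated meets every rule. The inconsistency should be corrected, but it does not threaten the study's design.

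**What to change.** In SAP Sections 3, 6 and 10, replace every enrolment or ITT sentence with the protocol Section 5.3 definition: informed consent plus attempted catheter insertion. Section 5.1 already agrees. Use that one set as the denominator of the primary endpoint and of every table labelled ITT.

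Tabulate the four-week safety follow-up of endoscopic screen failures in its own table, outside the primary proportion. If the sponsor wants a wider or narrower safety set, give it a different name and justify it as a departure from the protocol. Check the cross-reference to protocol Section 11.3 at the same time.

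The cost is SAP wording only, with no new data and no protocol amendment. The reported SAE rate, or its upper limit, may look slightly less favourable.
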